## 2.2.1 Pre-Clinical Development

In intravenous (IV) repeat-dose toxicology studies in cynomolgus monkeys, nivolumab alone was well tolerated (Investigator Brochure, 2014). Nivolumab bound specifically to PD-1 (and not to related members of the CD28 family such as CD28, ICOS, CTLA-4, and BTLA) with a  $K_d = 3.06$  nM. A surrogate rat anti-mouse PD-1 antibody (4H2) was derived and expressed as chimeric IgG1 murine antibody. Antitumor activity was seen for several tumor models, including colon carcinoma and fibrosarcoma.

## 2.2.2 Clinical Development

Nivolumab is being evaluated as monotherapy and in combination with cytotoxic chemotherapy, other immunotherapy (such as ipilimumab), anti-angiogenesis therapy, and targeted therapies in completed and ongoing BMS-sponsored clinical trials in NSCLC, melanoma, RCC, hepatocellular carcinoma (HCC), gastrointestinal (GI) malignancies including microsatellite instability (MSI) in colorectal cancer, and triple-negative breast cancer (TNBC) with an expanding group of indications (Investigator Brochure, 2014). In addition, two investigator-sponsored trials (ISTs) of nivolumab in combination with a peptide vaccine in melanoma are being conducted in the adjuvant setting and advanced disease. Seven nivolumab studies were conducted in Japan, including six studies in advanced solid tumors and recurrent or unresectable stage III/IV melanoma sponsored by Ono Pharmaceuticals Co. Ltd., and one IST in recurrent or advanced platinum-refractory ovarian cancer.

#### 2.2.3 Pharmacokinetics

Pharmacokinetics (PK) of nivolumab were linear in the range of 0.3 to 10 mg/kg, with doseproportional increases in maximum serum concentration ( $C_{max}$ ) and area under the concentrationtime curve from time zero to infinity (AUC0-∞), with low to moderate inter-subject variability observed at each dose level (Investigator Brochure, 2014). Clearance of nivolumab is independent of dose in the dose range (0.1 to 10 mg/kg) and tumor types studied. Body weight normalized dosing showed approximately constant trough concentrations over a wide range of body weights. The mean terminal elimination half-life of BMS-936558 is 17 to 25 days consistent with the halflife of endogenous IgG4.

#### 2.2.4 Efficacy

In a phase 1 (1, 3, and 10 mg/kg nivolumab doses) dose-escalation study the 3 mg/kg dose was chosen for expanded cohorts. Among 236 patients, objective responses (ORs) (complete or partial responses [CR or PR]) were seen in NSCLC, melanoma, and RCC. ORs were observed at all doses

[44]. Median OS was 16.8 months across doses and 20.3 months at the 3 mg/kg dose. Median OS across all dose cohorts was 9.2 months and 9.6 months for squamous and non-squamous NSCLC, respectively [45]. In the RCC cohort, median duration of response was 12.9 months for both doses with 5 of the 10 responses lasting  $\geq$ 1 year (Drake et al., 2013).

In a phase 1 study of nivolumab plus platinum-based doublet chemotherapy (PT-doublet) in chemotherapy-naïve NSCLC patients, 43 patients were treated with nivolumab + PT-doublet [46]. No dose-limiting toxicities (DLTs) were reported and total/confirmed ORRs were 43/33%, 40/33%, and 31/31% in nivolumab/gemcitabine/cisplatin, nivolumab/pemetrexed/cisplatin, and nivolumab/carboplatin/paclitaxel arms, respectively.

# 2.2.4.1 Activity in Lymphomas

In a phase 1 study of 23 heavily treated patients with relapsed or refractory Hodgkin's lymphoma were treated with 3 mg/kg nivolumab every 2 wks [47]. This resulted in an objective response in 20 subjects, including 4 subjects with a complete response, and progression-free survival of 86% at 24 wks. Copy-number gains in PDL1 and PDL2 gene resulted in enhanced JAK-STAT activity, which may explain the activity seen.

A phase I study of nivolumab in patients with relapsed or refractory lymphoid malignancies included 29 subjects with B-NHL and 23 patients with T-NHL, resulting in overall response rates of 28% and 17%, respectively [48]. This study, as well as two previous studies with pidilizumab in subjects with follicular lymphoma or diffuse large B cell lymphoma confirm the safety of this approach [49, 50].

#### 2.2.5 Toxicology

A maximum tolerated dose (MTD) of nivolumab was not defined [51]. Serious adverse events (SAEs) occurred in 32 of 296 patients (11%) similar to the immune-related inflammatory events seen with ipilimumab: pneumonitis, vitiligo, colitis, hepatitis, hypophysitis, and thyroiditis (with noted pulmonary toxicity resulting in 3 deaths. Renal failure, symptomatic pancreatic and DM, neurologic events, and vasculitis have also been reported.).

It is recognized that HTLV-1 is associated with inflammatory diseases, whose etiology is unclear. These include forms of myelopathy, uveitis, arthropathy, pneumonitis, and Sjogren's disease-like manifestations. Aberrant immune responses resulting in cross-reaction between virus-induced antigens and cellular antigens may be at least partially responsible. Thus, there is a theoretical risk that immune checkpoint inhibitors may promote these disorders, to which there will be careful attention.

#### 2.2.6 Pharmacodynamics/Biomarkers

Tumor-cell expression (melanoma) of PD-L1 was characterized with the use of IHC staining and pharmacodynamics changes in the peripheral-blood absolute lymphocyte count (Wolchok et al., 2013). With PD-L1 positivity defined as expression in at least 5% of tumor cells, biopsy specimens

from 21 of 56 patients (38%) were PD-L1–positive. Among patients treated with the concurrent regimen of nivolumab and ipilimumab, ORs were observed in patients with either PD-L1–positive tumor samples (6 of 13 patients) or PD-L1–negative tumor samples (9 of 22). In the sequenced regimen cohorts, a higher number of overall responses was seen among patients with PD-L1–positive tumor samples (4 of 8 patients) than among patients with PD-L1–negative tumor samples (1 of 13) suggesting the possibility that these tumors have higher response rates to the combination. Tissue expression of PDL-2, interferon- $\gamma$  (IFN- $\gamma$ ), IDO, and T cell CD8+ are of current interest. Until more reliable data based on standardized procedures for tissue collection and assays are available, PD-L1 status cannot be used to select patients for treatment at this time. Recent findings suggest a possible correlation to higher mutational load and expression of a subset of mutant tetrapeptide motifs in tumor antigens [52].

#### 2.3 Rationale

The rationale for the use of nivolumab in HTLV-1 associated ATLL is to enhance immune clearance of infected malignant cells.

#### 2.4 Correlative Studies Background

See Section 2.1 for HTLV-1 Proviral DNA and Cell-Associated and Virion RNA Load and Protein Expression (2.1.2), HTLV-1 Clonality (2.1.3) and HTLV-1 Immune Responses (2.1.7).

See Section 2.2 for Pharmacodynamics/Biomarkers (2.2.6).

#### **3. PATIENT SELECTION**

#### 3.1 Inclusion Criteria

- 1. Patients with any stage of pathologically confirmed CD3+ acute, lymphoma, chronic, or smoldering subtypes of ATLL.
- Documentation of HTLV infection (ELISA) in individual with confirmation of HTLV-1 infection (by immunoblot or PCR) or a consistent clinical picture [including two of the following: 1) CD4+ leukemia or lymphoma, 2) hypercalcemia, and/or 3) Japanese, Caribbean or South American birthplace].
- 3. Patients with acute or lymphoma forms must have received at least one cycle of combination chemotherapy (with or without mogamulizumab) or interferon (with or without zidovudine and/or arsenic). Individuals with chronic or smoldering ATL are not required to have had prior treatment or could have received any number of previous courses of therapy.
- 4. ECOG performance status 0-2 (Karnofsky  $\geq 60\%$ , see Appendix A).
- 5. Age at least 18. Because no dosing or adverse event data are currently available on the

use of nivolumab in patients <18 years of age, children are excluded from this study, but will be eligible for future pediatric trials.

- 6. Life expectancy >12 weeks.
- 7. Patients must have normal organ and marrow function as defined below:
  - a. leukocytes  $\geq$  3,000/mcL
  - b. absolute neutrophil count  $\geq$  1,500/mcL
  - c. platelets  $\geq 100,000/mcL$
  - d. total bilirubin within normal institutional limits
  - e.  $AST(SGOT)/ALT(SGPT) \le 2.5 \times institutional upper limit of normal$
  - f. creatinine within normal institutional limits OR creatinine clearance  $\geq 60 \text{ mL/min/1.73} \text{ m}^2$  for patients with creatinine levels above institutional normal.
- 8. The effects of nivolumab on the developing human fetus are unknown. For this reason, women of child-bearing potential and men must agree to use adequate contraception (hormonal or 2 barrier methods of birth control; or abstinence) prior to study entry and for the duration of study participation. Women should continue birth control for 23 weeks after stopping nivolumab, and men should continue birth control for 31 weeks after stopping nivolumab. Should a woman become pregnant or suspect she is pregnant while she or her partner is participating in this study, she should inform her treating physician immediately. Men treated or enrolled on this protocol must also agree to use adequate contraception prior to the study, for the duration of study participation, and 31 weeks after completion of nivolumab administration.
- 9. Ability to understand and the willingness to sign a written informed consent document.

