## 2.1.1 HTLV-1 Associated Adult T-Cell Leukemia Lymphoma

Although HTLV-2 is not clearly associated with a clinical disorder, HTLV-1 is closely associated with two clinical disorders [1]. About 5% of HTLV-1 infected individuals eventually develop a form of myelopathy known as HTLV-1 myelopathy (HAM) or tropical spastic paraparesis (TSP). It is characterized by lower limb spasticity, bowel and bladder disturbances, and slow but steady progression over several years. HTLV-1 has also been associated with other inflammatory clinical conditions, including uveitis, arthropathy, myopathy, pneumopathy, and a Sjogren's disease-like syndrome [8]. Some investigators have suggested that these disorders are related to high virus load, overstimulation of dendritic cells, resulting in chronic production of high levels of type 1 interferons and interferon-stimulated gene expression.

About 5% of HTLV-1 infected individuals develop a T-cell non-Hodgkin's lymphoma designated adult T-cell leukemia lymphoma (ATLL). It occurs almost exclusively in individuals who acquired HTLV-1 as a result of breast feeding, although four or five decades are generally required before development of disease. ATLL is characterized by frequent blood and bone marrow involvement, hypercalcemia, and lytic bone lesions. It is most commonly a CD4+ leukemia/lymphoma, although occasional examples of CD8+ lymphoma have been described. ATLL may fit into a variety of pathological subtypes as classified by the International Working Party Formulation. Clinical classifications of ATLL have included a "smoldering" disorder characterized by rash and minimal blood involvement, as well as a chronic form of ATLL, which have median survivals of two years or more (Fig 1) [9]. In contrast, a "lymphomatous" form of ATLL and an "acute" form of ATLL have median survivals of 3-6 months.

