# 9.4.5 Protein Markers Associated with Sensitivity or Resistance to Nivolumab

Multiplex ELISA assays have been developed to analyze over 25 angiogenic, inflammatory and immune-related markers in less than 0.5 ml of plasma. Coefficients of variation for most analytes are <10%. This platform has been successfully applied to several in-house phase I and II studies, as well as several phase III, Alliance-conducted studies with bevacizumab in colorectal and other cancers at Duke University. Markers of inflammation will be analyzed in the Duke Phase I Biomarker Lab, which serves as a core lab for these analyses for the US Cooperative Group, the Alliance.

Analyses will be performed on pre-treatment and on-treatment plasma samples. Analyte levels, and changes in analyte levels, will be correlated with clinical outcome (PFS, OS). Plasma will also be evaluated for protein markers that may be associated with sensitivity or resistance to ibrutinib. These may include CRP and other markers of inflammation, including but not limited to IFN $\gamma$ , IL1 $\beta$ , IL6, sILR6R, sGP130, IL4, IL7, IL10, IL12, IL17A, IL17E, and IL23. Additional markers of proteins regulated by the PD-1/PD-L1 interaction and the IL6/JAK-STAT axis will also be assessed, including but not limited to VEGF, HER and TGF $\beta$  family members.

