#### 13.2 Study Design

At least 20 evaluable patients will be enrolled for this study. Evaluable patients will be those patients who received study medication. The sample size of 20 patients is based on Simon's Optimal 2-stage design, with the assumption that an overall response rate of 40% is the minimum response rate that would be considered for further analysis of this approach, compared to a rate of 10% under null hypothesis. Thus, 20 subjects are required to with a one-side type 1 error rate of 5% and a power of 90%. If 1 or fewer responses are seen among the first 9 subjects enrolled, the trial is stopped early for futility. In contrast, if 2 or more responders are observed out of the 9 patients in the first stage, additional 11 patients will be enrolled in the 2nd stage. In a multicenter study such as this, however, it is difficult for a trial to reach the planned sample exactly. The investigators would not turn away patients who have already been approached for participation just because the number of patients needed has been met. Therefore, we adopted a flexible Phase II design (Chen and Ng 1998) to allow the actual number at final stage to deviate slightly from

what is planned. Due to the expected relatively low accrual rate, we expect that the interim analysis could be performed at the designed sample size. Only the decision boundaries at the 2nd-stage are determined following Chen and Ng's flexible design and programed by the study statistician [57]. That is, if 5 or more responders are observed out of 20-23 patients, or 6 or more responders are observed out of 24-25 patients, we would conclude that preliminary evidence for efficacy exists and that further investigation of the treatment is warranted.

The interim analysis will be based upon independent review of response, with a minimum time frame of 2 months for the interim analysis. Accrual will not be halted during the interim analysis.

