#### 13.3 Data Analysis

Data analysis of the study will be descriptive in nature. Demographic and clinical characteristics of the sample, toxicity by grade, as well as tumor response, duration of response, and length of follow-up will be summarized using descriptive statistics. Binomial proportions and their 90% confidence intervals will be used to estimate the response rates of therapy. Binomial proportions and their 90% confidence intervals will also be calculated for the efficacy based on immune response criteria (Appendix D). The Kaplan-Meier method will be used to evaluate the response duration. Analysis of variance methods will be used to evaluate the effects of treatment and time on the viral load measurements, as well as measurements of viral transcripts. The incidence of toxicities will be estimated using the binomial proportion and its 90% confidence interval. A proportional hazards analysis with viral load measures as time dependent covariates will be used to evaluate the effects of treatment and structure the effects of these measures on duration of response. Detailed analysis of correlative studies and biomarkers are listed in Section 9.

The safety and tolerability will be monitored every 2 weeks. All patients who receive treatment with nivolumab will be eligible for safety and tolerability analysis. A Bayesian sequential monitoring method [58] will be used for safety analysis and the stopping rule is defined as  $Pr(\theta>0.10 | data)>0.90$ , where  $\theta$  denotes the proportion of patients who discontinue therapy due to intolerable toxicity. That is, enrollment will be stopped early whenever, given the accumulated observed data, there is >90% probability that the discontinuation of therapy is greater than 10%. Specifically, enrollment will be stopped early if 3 patients discontinue therapy in the first 12 patients, or 4 patients discontinue therapy in the first 19 patients, or 5 patients discontinue therapy before the last patient enrolled. These boundaries were obtained using the free-download software Multc99 (version 2.1) from M.D. Anderson Cancer Center. We assume that the parameter  $\theta$ follows a prior distribution of beta ( $\alpha$ ,  $\beta$ ), with  $\alpha$  and  $\beta$  representing the number of patients discontinuing and continuing therapy respectively.

	Ethnic Categories				T ( )
Racial Categories	Not Hispanic or Latino		Hispanic or Latino		Total
	Female	Male	Female	Male	
American Indian/ Alaska Native	0	0	0	0	0

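### Acute/lymphoma and chronic/smoldering ATLL are enrolled together, yet no subtype factor is specified for the response estimate or for the exploratory marker-survival analyses

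*Combined protocol and SAP*

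**What the plan says.** Eligibility (section 3.1, item 1) covers all four subtypes, with no cap or quota: "Patients with any stage of pathologically confirmed CD3+ acute, lymphoma, chronic, or smoldering subtypes of ATLL". Item 3 sets different entry conditions. Acute and lymphoma patients must already have had systemic treatment, whereas "Individuals with chronic or smoldering ATL are not required to have had prior treatment".

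Section 2.1.1 separates the subtypes by prognosis. The smoldering form is described as "characterized by rash and minimal blood involvement, as well as a chronic form of ATLL, which have median survivals of two years or more"; the lymphomatous and acute forms "have median survivals of 3-6 months".

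The design (section 13.2) uses one target rate of 40%, "compared to a rate of 10% under null hypothesis", with one futility look and one success boundary for all patients. In section 13.3, "Binomial proportions and their 90% confidence intervals will be used to estimate the response rates of therapy", with no split by subtype. Section 13.4.2 bases conclusions on all eligible patients, and the only subgroup analyses it mentions exclude patients with protocol deviations.

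For the markers, section 9.4.5 states: "Analyte levels, and changes in analyte levels, will be correlated with clinical outcome (PFS, OS". Section 9.4.4 compares overall survival curves by a log-rank test for which no strata are named. Section 9.4.4 also compares clinical groups, but does not define them.

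**The concern.** Subtype is known at entry, is strongly prognostic on the protocol's own figures, and is tied to prior treatment by the entry criteria. That makes it an obvious baseline confounder for any analysis relating a biomarker to PFS or OS. A link between markers and subtype is plausible from the text: smoldering disease involves little blood, while viral load and clonality are measured in PBMCs. If subtype is left out, a marker that only identifies aggressive disease can appear to predict outcome on nivolumab. Exploratory findings of this kind still shape later studies.

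For response, the pooled rate alone would not show whether responses were spread across both disease groups or confined to one.

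**Working it through.** **1. The design's own figures.** Inputs (13.2): null 10%, target 40%, continue if at least 2 of the first 9 respond, succeed if at least 5 of 20 respond.

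P(pass | p) = sum over x = 2 to 9 of Bin(x; 9, p) × P[Bin(11, p) ≥ 5 − x].

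- p = 0.10: 3.5% (limit 5%)
- p = 0.40: 90.2% (stated 90%)

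The stated sample size and stage rules reproduce. The sample-size arithmetic is sound.

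**2. Survival ratio.** From 2.1.1: 24/6 = 4 and 24/3 = 8, so the ratio is at least four-fold.

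**3. Marker with no effect within subtype.** The documents give no subtype mix, no marker difference and no censoring time, and 9.4.5 names no test. Assumed: 20 patients, exponential survival, medians 4.5 months (midpoint of 3-6) and 24 months, censoring at 24 months, a normally distributed marker whose mean differs between subtypes, and a Cox test at two-sided 5%. Simulated rejection rates (ranges cover a Cox fit with 1,500 runs and a score test with 3,000 runs):

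| Marker difference | Pooled, 10/10 | Pooled, 15 aggressive/5 indolent |
|---|---|---|
| 0.5 SD | 9-11% | 9% |
| 1 SD | 22-24% | 18% |
| 1.5 SD | 41-42% | 30% |

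Stratified by subtype, the rate is about 4-6% throughout.

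Sensitivity: with medians of 24 versus 3 or 6 months, 36-month censoring, and 10 or 5 patients in the smaller group, the pooled rate at 1 SD is 16-28%, against 5.4-6.2% when stratified. With an 18/2 mix under the main assumptions, the pooled rate at 1 SD falls to about 10%.

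**4. Response by subtype.** Take 5 responses in 20, which meets the success boundary, and suppose all 5 are indolent in a 10/10 mix. Exact 90% intervals:

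- pooled 5/20: 10-46%
- chronic/smoldering 5/10: 22-78%
- acute/lymphoma 0/10: 0-26%, with upper limit 1 − 0.05^(1/10) = 0.259

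The pooled figure hides this contrast. The subtype intervals show it, although they are wide.

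**5. Whether the duration-of-response model should also be stratified.** That model (13.3) uses responders only: 5 at the boundary, or 0.40 × 20 = 8 at the target rate. Assume a log-hazard of 1.0 per SD, median duration 13 months, 24-month censoring and no confounding. Stratification then cuts score-test power from 17% to 0% with 5 responders split 2/3, and from 41% to 28% with 8 split 3/5. Stratifying there is not workable.

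**The case against.** The marker work sits under section 9.4, headed as exploratory and ancillary, and 13.3 calls the analysis descriptive. Section 9.4.5 speaks only of correlation, so the Cox test and the 5% threshold are supplied here. The mix, marker difference and censoring are also assumed. The medians are background figures; the entry criteria (life expectancy over 12 weeks, ECOG 0-2, adequate organ function) may narrow the survival gap among enrolled patients. No sentence forbids a subtype term, and the undefined clinical groups in 9.4.4 might include subtype. All of this stands. It limits how firmly the size can be stated, but stratifying by a baseline factor costs almost nothing for OS with 20 patients.

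A reader might go further and infer that the pooled rule is faulty because it can pass on one subtype alone. At true response rates of 5% (aggressive) and 40% (indolent), it passes in about 42% of trials with a 10/10 mix and 74% with 5 aggressive and 15 indolent patients. The documents do not support that inference. One group has then reached the protocol's own 40% target, and 13.2 claims only preliminary evidence that justifies further study, with no subtype claim.

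A reader might also want the conclusion confined to the groups that showed responses. That would have no threshold: a group of 10 responding at the null 10% shows at least one response in 1 − 0.9^10 = 65% of trials. It would also conflict with 13.4.2, which rests conclusions on all eligible patients.

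**Conclusion.** The point holds as a gap in reporting and in control of confounding. The response estimate in 13.3 and the marker-survival analyses in 9.4.5 and 9.4.4 specify no subtype factor, although the protocol's own medians differ at least four-fold. Under the stated assumptions, a marker with no within-subtype effect is falsely flagged in about 9-42% of pooled analyses (10/10 mix) or 9-30% (15 aggressive/5 indolent), against about 4-6% when stratified. The size depends on the mix, the marker difference and the survival gap among enrolled patients, none of which the documents give. It shrinks if one subtype dominates enrolment.

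It does not follow that any marker differing between subtypes will necessarily correlate with survival: at 1 SD most pooled analyses would still be non-significant. Nor do the simulations represent the time-dependent viral-load model for response duration, because 2.1.1 gives survival by subtype, not response duration.

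**What to change.** - **13.2 and 13.4.2:** no change. Keep the pooled two-stage rule and the conclusion based on all eligible patients, and do not tie the efficacy conclusion to whichever group shows a response.
- **13.3:** add that the response rate will also be reported descriptively for acute/lymphoma and for chronic/smoldering ATLL, each with an exact 90% interval beside the pooled rate and without a subtype hypothesis test. Leave the responder-only duration model unstratified and list each responder's subtype with the duration.
- **9.4.5 and 9.4.4:** add that analyses relating markers or the neoantigen signature to PFS or OS, including the log-rank comparison, will be stratified by this two-level subtype.

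The cost is a few sentences; no extra patients or data are needed, since subtype is already established at entry. The downside is wide subtype intervals, as the 0-26% and 22-78% examples show. Specifying the split now avoids choosing it after the results are known.

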# 11.1.1 Definitions

Evaluable for toxicity. All patients will be evaluable for toxicity from the time of their first treatment with nivolumab.

Evaluable for objective response. Only those patients who have measurable disease present at baseline, have received at least one cycle of therapy, and have had their disease re-evaluated will be considered evaluable for response. These patients will have their response classified according to the definitions stated below. (Note: Patients who exhibit objective disease progression prior to the end of cycle 1 will also be considered evaluable.)

Evaluable Non-Target Disease Response. Patients who have lesions present at baseline that are evaluable but do not meet the definitions of measurable disease, have received at least one cycle of therapy, and have had their disease re-evaluated will be considered evaluable for non-target disease. The response assessment is based on the presence, absence, or unequivocal progression of the lesions.

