#### **13.4.2** Evaluation of Response

All patients included in the study must be assessed for response to treatment, even if there are major protocol treatment deviations or if they are ineligible. Each patient will be assigned one of the following categories: 1) complete response, 2) partial response, 3) stable disease, 4) progressive disease, 5) early death from malignant disease, 6) early death from toxicity, 7) early death because of other cause, or 8) unknown (not assessable, insufficient data). [Note: By arbitrary convention, category 8 usually designates the "unknown" status of any type of data in a clinical database.]

All of the patients who met the eligibility criteria (with the possible exception of those who received no study medication) should be included in the main analysis of the response rate. Patients in response categories 4-9 should be considered to have a treatment failure (disease progression). Thus, an incorrect treatment schedule or drug administration does not result in exclusion from the analysis of the response rate. Precise definitions for categories 4-9 will be protocol specific.

All conclusions should be based on all eligible patients. Subgroup analyses may then be performed on the basis of a subset of patients, excluding those for whom major protocol deviations have been identified (*e.g.*, early death due to other reasons, early discontinuation of treatment, major protocol violations, etc.). However, these subgroup analyses may not serve as the basis for drawing conclusions concerning treatment efficacy, and the reasons for excluding patients from the analysis should be clearly reported. The 95% confidence intervals should also be provided.

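### No entry criterion requires ATLL to be present and assessable at baseline, and Sections 11.1.1, 13.2 and 13.4.2 disagree on whether a patient in remission counts in the response rate

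*Combined protocol and SAP*

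**What the plan says.** **Entry.** Item 1 of Section 3.1 admits "Patients with any stage of pathologically confirmed CD3+ acute, lymphoma, chronic, or smoldering subtypes of ATLL". Item 3 adds that "Patients with acute or lymphoma forms must have received at least one cycle of combination chemotherapy" or interferon. It does not ask how the disease responded. Chronic and smoldering types may be untreated or may have had any number of courses. Section 3.2 sets a 4-week washout from chemotherapy or radiotherapy (6 weeks for nitrosoureas and mitomycin C). Nothing in the 9 inclusion or 16 exclusion items refers to active, measurable, evaluable, relapsed or refractory disease.

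**Who counts for response.**
- Section 11.1.1: "Only those patients who have measurable disease present at baseline", who have also had a cycle of therapy and a re-evaluation, are evaluable for objective response. A separate category covers lesions that are evaluable but not measurable.
- Section 13.2: a patient is evaluable once dosed.
- Section 13.4.2: "All patients included in the study must be assessed for response to treatment". The main response-rate analysis takes all eligible patients, with a possible exception for those never treated, and treats the not-assessable category as failure.

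**How response is scored.** The table in Section 11.1.4 covers nodes, extranodal masses, spleen and liver, skin, blood and marrow. Its complete-remission row is defined by all disease having disappeared, and each compartment must be normal.

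**Design.** Section 13.2 tests 40% as the target, "compared to a rate of 10% under null hypothesis", with an interim rule: "If 1 or fewer responses are seen among the first 9 subjects enrolled, the trial is stopped early for futility".

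**The concern.** Overall response rate is the efficacy half of the primary objective. A patient with no detectable ATLL at baseline carries no information about it, because no compartment can show a decrease. The entry criteria let such a patient in, and the analysis sections then give different answers on whether the patient belongs in the denominator. Under Sections 13.2 and 13.4.2 the patient stays in and, without a complete or partial response, counts against the drug. Under Section 11.1.1 the patient is left out.

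With 20 patients, a stage 1 cut at 1 of 9 and a final boundary of 5, the design has little slack. One or two uninformative patients change its operating characteristics, most of all if they fall among the first 9.

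**Working it through.** **Inputs from Section 13.2.** Null rate 10%; target rate 40%; "one-side type 1 error rate of 5% and a power of 90" per cent; 9 patients in stage 1, stopping at 1 or fewer responses; 11 more in stage 2; success at 5 or more of 20. **Assumption:** the number of disease-free patients. No section gives it, so 1 and 2 of 20 are shown.

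**Step 1: reproduce the plan.** With X ~ Bin(9, p) and Y ~ Bin(11, p),

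P(success) = Σ over x = 2 to 9 of P(X = x) · P(Y ≥ 5 − x).

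- At p = 0.40: 0.1612 × 0.8811 + 0.2508 × 0.9698 + 0.2508 × 0.9964 + 0.2666 = 0.1421 + 0.2432 + 0.2499 + 0.2666 = 0.902.
- At p = 0.10: 0.0154 + 0.0135 + 0.0051 + 0.0009 = 0.0349.

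The stated 90% power and 5% limit are reproduced. A search over two-stage designs also returns 9 + 11 as Simon's optimal design.

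**Step 2: disease-free patients as non-responders.** With j of them in stage 1 and m in stage 2, replace the distributions by X ~ Bin(9 − j, p) and Y ~ Bin(11 − m, p), and leave the boundaries unchanged. For j = 1, m = 0, p = 0.40:

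0.2090 × 0.8811 + 0.2787 × 0.9698 + 0.2322 × 0.9964 + 0.1737 = 0.860 (to rounding).

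The chance of a wrong stage 1 stop at 40% rises from 7.1% to 0.6⁸ + 8 × 0.4 × 0.6⁷ = 0.0168 + 0.0896 = 10.6%.

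**Step 3: the conditional case of a complete-remission score.** Use the same reduced distributions, but add j to the stage 1 count and m to the stage 2 count, and evaluate at p = 0.10.

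| Disease-free patients (stage 1 + stage 2) | Power at 40%, as non-responders | Error at 10%, if scored as complete remission |
|---|---|---|
| 0 + 0 | 90.2% | 3.5% |
| 0 + 1 | 88.9% | 8.3% |
| 1 + 0 | 86.0% | 10.7% |
| 0 + 2 | 87.2% | 15.9% |
| 1 + 1 | 84.4% | 23.6% |
| 2 + 0 | 80.1% | 26.6% |

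Averaged over random placement among the 20, one such patient gives power 87.6% or error 9.4%, and two give 84.4% or 21.9%.

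**Step 4: the sections side by side for one treated patient in remission.**

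| Section | Status of the patient |
|---|---|
| 3.1, 3.2 | Eligible |
| 11.1.1 | Not evaluable for objective response |
| 13.2 | Evaluable, because dosed |
| 13.4.2 | In the main analysis; a failure if not assessable |
| 11.1.4 | No rule for absent baseline disease |

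**The case against.** **Complete remission by default.** A reader might infer that a patient in remission would be scored automatically as a complete responder, because each organ cell of that row would be normal from the first assessment. The documents do not say so. The row is defined by disease having disappeared, which presupposes disease at baseline. Section 11.1.1 would call the patient not evaluable, and Sections 11.1.7 and 13.2 provide for independent review of response. The score is a possible misreading, so the error figures above are conditional on it.

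**Section 11.1.1 already deals with the case.** It does offer a third outcome, exclusion from the response-evaluable set. But it conflicts with Sections 13.2 and 13.4.2, and excluding patients changes the denominator: the final boundaries in Section 13.2 start at 20, and the interim counts the first 9 enrolled. Its measurable-disease wording also does not suit leukemic patients or some skin-only patients, whom the 11.1.4 table assesses by blood, marrow and skin.

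**Such patients may be few.** Section 2.1.5 reports complete responses to chemotherapy of only about 30%, not durable, and 11% in one EPOCH series. Section 2.1.1 gives median survivals of 3-6 months for the acute and lymphoma forms. This stands: the count is unknown, and one patient counted as a failure costs only 1.3 to 4.2 points of power.

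**They are informative for safety.** This also stands. Safety and tolerability are part of the primary objective, and every treated patient contributes to them.

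**Entry already implies disease.** Item 1 speaks of patients with pathologically confirmed ATLL, and tumor measurements and marrow are scheduled before treatment. But confirmation of the diagnosis carries no date, and a scheduled baseline procedure is not an eligibility criterion.

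**Conclusion.** The gap is real. As written, a patient in remission after prior therapy can be enrolled. Sections 13.2 and 13.4.2 then count that patient in the response rate, Section 11.1.1 does not, and no rule fixes the score.

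The consequence the text supports is loss of power. At a 40% response rate, power falls from 90.2% to 86.0-88.9% with 1 such patient of 20, and to 80.1-87.2% with 2. The ranges reflect how the patients fall between the stages. Inflation of the one-sided error from 3.5% to 8.3-10.7% (1 patient) or 15.9-26.6% (2 patients) follows only if the table is misread. It is a reason to close the gap, not a property of the plan.

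All these figures assume 20 patients, independent responses and unchanged boundaries. The number of patients in remission is an assumption that the documents cannot settle.

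**What to change.** 1. Add an inclusion item to Section 3.1: ATLL must be assessable at baseline in at least one compartment of the 11.1.4 table (nodes, extranodal masses, spleen or liver, skin, blood or marrow). Add the matching line to the eligibility checklist.
2. Align Section 11.1.1 with Sections 13.2 and 13.4.2, so that all treated patients who meet this item form the response-rate denominator, including leukemic and skin-only patients. The entry item alone would leave those patients in conflict with the measurable-disease wording.

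No further requirement of persistent, relapsed or progressive disease after the most recent therapy is needed. It would narrow the population beyond what the problem calls for.

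The cost is one amendment covering an inclusion item and a definition, plus one checklist line. The sample size and boundaries stay as they are, and the calculated power of 90.2% and error of 3.5% are kept. The downside is that a few patients in remission who could have contributed safety data are not enrolled. The change should come before such patients enter, because removing them later would be a post hoc exclusion.
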